9.4 Treatment Schedule

Each participant received eight supervised treatment sessions over four weeks, with two sessions per week. Each session lasted approximately 15 to 20 minutes.

10. Outcomes and Assessment Schedule

Outcomes were assessed at baseline, immediately after the four-week intervention, and at three-month follow-up. The primary outcome was headache pain intensity measured using the Numeric Pain Rating Scale. Secondary outcomes were headache frequency per week, neck pain intensity, Neck Disability Index score, Depression Anxiety Stress Scale-21 stress, anxiety and depression scores, and Short Form-12

physical and mental component scores. Detailed outcome measure definitions are entered separately in the ClinicalTrials.gov record.

11. Sample Size

The sample size was calculated using power analysis based on headache pain intensity as the primary outcome. Using an effect size derived from a similar study, with power of 0.90 and alpha of 0.05, the required sample size was 64 participants, with 32 participants per group.

12. Data Collection and Management

Baseline demographic and clinical data were collected using a structured questionnaire. Clinical outcomes were collected using validated self-administered questionnaires and scales at the pre-specified assessment time points. Data were treated confidentially and stored securely. Hard-copy data were kept in a locked file cabinet, and electronic data were kept on a password-protected computer according to institutional procedures.

13. Safety Monitoring

Participants were screened for contraindications to cervical mobilization before enrolment. Participants were informed that participation was voluntary and that they could withdraw at any time without penalty. Any unexpected symptoms or adverse responses during treatment were to be managed by the study team according to clinical judgment and institutional procedures.

14. Statistical Analysis Plan

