14.4 Outcome Analysis

Multivariate analysis of variance was used to examine between-group differences in outcome measures at the assessment points. When multivariate tests were statistically significant, independent-samples t-tests were conducted for individual outcome variables. The significance level was set at $p < 0.05$, one-tailed. Analyses were performed using IBM SPSS Version 25.

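### Section 14.4 allows a t-test of the primary outcome only after a significant multivariate test, so the primary hypothesis can go untested and the 0.90 power is not established for the procedure described

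*Combined protocol and SAP*

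**What the plan says.** Section 3 names a single primary objective, the effect on headache pain intensity. Section 10 agrees: "The primary outcome was headache pain intensity measured using the Numeric Pain Rating Scale". Section 11 sizes the trial on the same variable: "The sample size was calculated using power analysis based on headache pain intensity as the primary outcome", "with power of 0.90 and alpha of 0.05", and concludes that "the required sample size was 64 participants, with 32 participants per group". The effect size appears only as "Using an effect size derived from a similar study", with no value.

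Section 10 lists eight secondary scores: "Secondary outcomes were headache frequency per week, neck pain intensity, Neck Disability Index score, Depression Anxiety Stress Scale-21 stress, anxiety and depression scores", plus the SF-12 "physical and mental component scores". With NPRS that makes nine outcomes.

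Section 14.4 is the only between-group outcome analysis. It describes a MANOVA on the outcome measures and then states: "When multivariate tests were statistically significant, independent-samples t-tests were conducted for individual outcome variables". The level is 0.05, one-tailed. The section does not list the variables in the MANOVA, say how many models were fitted, or say what happens to NPRS if the multivariate test is not significant. No section names a primary time point.

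**The concern.** Sections 3, 10 and 11 give NPRS a special position, and section 14.4 takes it away. Under the rule as written, whether the primary hypothesis is tested depends on a joint test that also involves neck pain, disability, distress and quality-of-life scores. Two consequences follow.

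- If the multivariate test is not significant, the plan describes no test of NPRS, even where the NPRS difference alone would have been significant.
- A gated test cannot have more power than the same test without the gate. A sample size computed on NPRS alone therefore does not carry its 0.90 over to the gated procedure.

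A significant MANOVA also says only that the arms differ on some combination of scores, which is not the primary question.

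**Working it through.** **Inputs.** From section 11: n = 32 per group, power 0.90, alpha 0.05 (sidedness not stated). From section 10: one primary and eight secondary outcomes, p = 9. From section 14.4: the gate, and one-tailed testing at 0.05. Assumed, because the documents do not give them: standardised effect d, correlations, effects on the secondary outcomes, which variables enter the MANOVA, and no dropout. An F-test on nine outcomes has no direction, so I took the gate as the ordinary F-test at 0.05.

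**Step 1: the plan's own figure.** With no stated effect size, 32 per group cannot be reproduced, only back-solved. The t-test has 62 degrees of freedom and noncentrality d × √(n/2) = d × √16 = 4d.

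- One-tailed 0.05: d = 0.74, noncentrality 2.96, power 0.90.
- Two-sided 0.05: d = 0.823, noncentrality 3.29, power 0.90.

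Both are consistent with section 11 and both describe an ungated test.

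**Step 2: the gate alone.** A two-group MANOVA is Hotelling's T². The F-test has p = 9 and 2n − p − 1 = 64 − 10 = 54 degrees of freedom, and noncentrality (n/2) × D² = 16 × D², where D² is the squared Mahalanobis distance between the arms. If the other eight outcomes add no discriminating information, D² = d²:

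- d = 0.74: D² = 0.548, noncentrality 8.76, gate power 0.43.
- d = 0.823: D² = 0.677, noncentrality 10.84, gate power 0.53.

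In this case the gate alone would need about 77 or 63 per group, respectively, for 0.90 power. At 32 per group it reaches 0.90 only if D is at least 1.20.

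**Step 3: gate and NPRS t-test together.** With a common correlation ρ and standardised effects δ,

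D² = [Σδ² − ρ(Σδ)² / (1 + 8ρ)] / (1 − ρ).

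Example, NPRS only, d = 0.823, ρ = 0.3: D² = 0.677 × (1 − 0.3/3.4) / 0.7 = 0.88, giving gate power 0.67 and joint power 0.65. Joint power is by simulation with at least 20,000 replicates per cell (standard error at most √(0.25/20,000) = 0.0035).

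| Effect on the eight secondary outcomes | d = 0.74, one-tailed; ρ = 0 / 0.3 / 0.5 | d = 0.823, two-sided; ρ = 0 / 0.3 / 0.5 |
|---|---|---|
| none | 0.42 / 0.54 / 0.69 | 0.52 / 0.65 / 0.78 |
| half of d | 0.86 / 0.48 / 0.42 | 0.89 / 0.58 / 0.52 |
| equal to d | 0.90 / 0.83 / 0.69 | 0.90 / 0.88 / 0.78 |

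**Step 4: sensitivity to what the documents leave open.**

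- *Sized two-sided, tested one-tailed.* Ungated power is about 0.946. Joint power at ρ = 0 / 0.3 / 0.5 is 0.53 / 0.66 / 0.81 with no secondary effects, 0.93 / 0.59 / 0.53 with half effects, and 0.945 / 0.92 / 0.81 with equal effects.
- *Both follow-ups in one model (18 variables).* Gate power when the other variables add nothing falls to 0.27 (d = 0.74) or 0.34 (d = 0.823).
- *A smaller model (three variables).* With d = 0.823, two-sided, and secondary effects of 0.4 SD, joint power is about 0.76 to 0.86.
- *Dropout.* Section 11 states no allowance. An assumed 10% or 20% loss (29 or 26 per group) lowers even the ungated power to about 0.87 or 0.83.

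**The case against.** The strongest reply is that the size of the loss is assumed. The documents give no effect size, standard deviations, correlations or secondary effects, and section 14.4 does not say that all nine outcomes entered one MANOVA. Favourable cases exist: equal effects on uncorrelated outcomes leave power at 0.90, and a trial sized two-sided but tested one-tailed can stay above 0.90 with the gate in place. This stands. A reader might infer that the trial does not have its stated power. The documents do not support that; they support only that 0.90 was set for a different test.

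A reader might also infer that the primary hypothesis did go untested. The document reports no results, so it shows that this could happen, not that it did.

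It would be too simple to say that the secondary outcomes merely add noise. In the table, correlated outcomes with no effect raise joint power from 0.52 at ρ = 0 to 0.78 at ρ = 0.5. Section 3 also makes differences on the other outcomes secondary objectives, so a joint test is not foreign to the trial.

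Finally, the trial is completed and section 14.4 is written in the past tense. Replacing its rule would overwrite the record with an analysis chosen after the data existed. This stands too and shapes the remedy.

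None of this supplies a route to testing NPRS when the multivariate test is not significant.

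**Conclusion.** The structural point holds without any numerical assumption: sections 3, 10 and 11 rest on NPRS, and section 14.4 lets it be tested only through a multivariate gate with no exemption. Following the text can end the trial without a test of its primary hypothesis.

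On power, the supportable statement is that 0.90 refers to NPRS alone and is not established for the gated procedure. Under the step 3 assumptions, joint power is about 0.42 to 0.90. It is near 0.90 only in favourable cases, such as near-uncorrelated outcomes with sizeable secondary effects, or equal effects on all outcomes at low correlation. Fewer MANOVA variables would shrink the loss and 18 would enlarge it. A single figure for the trial's actual power would go beyond the documents.

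**What to change.** Because the trial is completed, this is a correction to reporting and wording:

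1. Report the between-arm NPRS comparison with its confidence interval at both 4 weeks and 3 months, whatever the MANOVA shows.
2. State which time point is treated as primary, and that the plan did not name one.
3. Keep the MANOVA as supportive output, or confine it to the secondary outcomes.
4. Leave the section 14.4 rule on record, disclose it, and label the ungated NPRS analysis as post hoc.
5. State that the 0.90 in section 11 applies to the ungated NPRS test.

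Possible wording:

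> The between-group difference in headache NPRS is reported with its confidence interval at 4 weeks and 3 months irrespective of the multivariate result. This ungated analysis is post hoc: section 14.4 made tests of individual outcomes conditional on a significant multivariate test, and no primary time point was named. The power of 0.90 in section 11 refers to the ungated comparison.

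The cost is one simple comparison per time point on data already held, and a few sentences. The downside is that the weak omnibus protection no longer covers the primary test. Baseline adjustment and a Holm correction for the secondary outcomes are separate matters and are not needed here.

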ClinicalTrials.gov Study Document

Study Protocol and Statistical Analysis Plan

Official Title

The Effectiveness of Passive Physiological Intervertebral Movements in Patients With Cervicogenic Headache: A Randomized Clinical Trial

NCT Number	Pending assignment - replace with the assigned NCT number before final public posting if required by PRS
Document Date	20 May 2026
Version	1.0
Study Status	Completed; retrospective ClinicalTrials.gov registration preparation
Sponsor/Institution	Jordan University of Science and Technology
IRB Approval	Jordan University of Science and Technology Institutional Review Board, Approval No. 73/148/2022

Public posting note: This document was prepared for ClinicalTrials.gov public posting. It does not include participant names or individual participant identifiers.

1. Protocol Synopsis

Condition	Cervicogenic headache
Study Design	Assessor-blinded, parallel-group randomized clinical trial
Allocation	Randomized allocation to two intervention arms
Intervention Model	Parallel assignment
Planned/Actual Enrollment	64 participants, 32 per arm
Setting	Outpatient physiotherapy departments of Jordan University of Science and Technology and King Abdullah University Hospital
Study Period	May 2022 to August 2025
Treatment Duration	Eight supervised sessions over four weeks
Assessment Time Points	Baseline, immediately after the four-week intervention, and three-month follow-up
Experimental Arm	Passive Physiological Intervertebral Movements plus therapeutic exercise
Comparator Arm	Therapeutic exercise alone

2. Background and Rationale

Cervicogenic headache is a secondary headache disorder associated with dysfunction in the cervical spine, particularly the upper cervical segments. Patients may experience headache, neck pain, restricted cervical movement, disability, psychological symptoms, and reduced quality of life. Therapeutic exercise and manual therapy are commonly used in physiotherapy management. Passive Physiological Intervertebral Movements are manual therapy techniques used to assess and improve segmental mobility. The study evaluated whether adding these movements to a standardized exercise program provides additional benefit compared with exercise alone.

3. Objectives

The primary objective was to determine the effect of adding Passive Physiological Intervertebral Movements to therapeutic exercise on headache pain intensity among participants with cervicogenic headache.

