14.2 Descriptive Statistics

Continuous variables were summarized using means and standard deviations. Categorical variables were summarized using frequencies and percentages. Baseline characteristics and baseline clinical measures were compared between groups to assess group comparability after randomization.

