14.3 Baseline Comparisons

Independent-samples t-tests were used to compare continuous baseline variables between groups. Chi-square tests were used to compare categorical baseline variables between groups.

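### The outcome analysis names no baseline covariate although every outcome is measured at baseline, which gives up precision and leaves any chance baseline difference in the estimated effect

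*Combined protocol and SAP*

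**What the plan says.** Section 10 schedules all outcomes, including the primary outcome (headache intensity on the Numeric Pain Rating Scale), at baseline, at four weeks and at three months.

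Section 14.4 gives the treatment comparison in two steps. First: "Multivariate analysis of variance was used to examine between-group differences in outcome measures at the assessment points". Then, if the multivariate test is significant, "independent-samples t-tests were conducted for individual outcome variables". The criterion is: "The significance level was set at $p < 0.05$, one-tailed". Neither step names a covariate, a change score or a repeated-measures term.

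Baseline values appear elsewhere only as a check on the randomisation. Section 14.2 states: "Baseline characteristics and baseline clinical measures were compared between groups to assess group comparability after randomization". Section 14.3 gives the tests: "Independent-samples t-tests were used to compare continuous baseline variables between groups", with chi-square tests for categorical variables. No rule connects the result of these tests to the outcome model.

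**The concern.** A baseline measurement of the same scale is usually the best single predictor of a follow-up score. If it is left out of the model, the variation it explains stays in the error term and the confidence interval is wider than it need be. A chance difference between arms at baseline is also carried, in proportion to the correlation, into the difference at follow-up.

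The comparability tests do not help with either problem. Under proper randomisation any baseline difference is due to chance, so the tests address a hypothesis already known to be true. A non-significant result does not show that the difference is too small to matter, and a significant one triggers no action in the plan. With 32 per arm, a baseline difference large enough to affect the reading of the trial can pass such a test.

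**Working it through.** **Inputs from the documents.** Section 1: "64 participants, 32 per arm". Section 11: "with power of 0.90 and alpha of 0.05, the required sample size was 64 participants, with 32 participants per group". Section 14.4: one-tailed 0.05. The effect size is described only as follows: "Using an effect size derived from a similar study".

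**Inputs assumed.** The correlation r between baseline and follow-up is not given; I use 0.3, 0.5 and 0.7. The SD is taken as equal in both arms and at both times, and all 64 participants are taken to contribute data.

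**1. The plan's own figure.** Because neither the effect size nor the SD is given, 64 cannot be reproduced forwards. Solving backwards for 90% power with 32 per arm (noncentral t, 62 df) gives d = 0.74 one-sided or d = 0.82 two-sided. The figure of 64 is therefore consistent with an unadjusted two-group t-test. Section 11 does not state the number of sides, so I use 0.74, which matches the one-tailed test in Section 14.4.

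**2. Precision.** ANCOVA multiplies the residual variance by 1 − r². The equivalent unadjusted size per arm is 32/(1 − r²). Power uses the noncentrality d/√(1 − r²) × √(32/2) with 61 df.

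| r (assumed) | 1 − r² | Variance cut | Equivalent n per arm | One-sided power, d = 0.74 |
|---|---|---|---|---|
| none (unadjusted) | 1 | – | 32 | 0.90 |
| 0.3 | 0.91 | 9% | 32/0.91 = 35 | 0.92 |
| 0.5 | 0.75 | 25% | 32/0.75 = 43 | 0.96 |
| 0.7 | 0.51 | 49% | 32/0.51 = 63 | 0.99 |

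Starting from d = 0.82 two-sided gives almost the same picture: 0.90 rising to 0.92, 0.96 and 0.995. These are powers for one outcome tested alone. They are not the power of the full procedure, in which the t-tests follow only after a significant MANOVA.

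**3. If change scores were used.** Their variance is 2(1 − r) in units of SD²: 1.4, 1.0 and 0.6 at the three correlations, against 0.91, 0.75 and 0.51 for ANCOVA. Since 1 − r² = (1 − r)(1 + r) and 1 + r ≤ 2, a change score is never more precise than ANCOVA. Below r = 0.5 it is less precise than the raw score.

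**4. Chance imbalance.** The standard error of the baseline difference is √(2/32) = 0.25 SD. About 32% of randomisations give a difference beyond 0.25 SD in one direction or the other. The two-sided baseline t-test becomes significant only at 1.999 × 0.25 = 0.50 SD, so a difference of 0.25 SD passes it easily. Given such a difference, the unadjusted follow-up difference is expected to shift by r × 0.25.

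The conditional one-tailed error at nominal 5% is P(Z > (1.645 − r × imbalance/0.25)/√(1 − r²)).

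| r (assumed) | Shift at 0.25 SD | Error, imbalance favours experimental arm | Error, imbalance favours comparator |
|---|---|---|---|
| 0.3 | 0.08 SD | P(Z > 1.345/0.954) = 0.079 | P(Z > 1.945/0.954) = 0.021 |
| 0.5 | 0.13 SD | P(Z > 1.145/0.866) = 0.093 | P(Z > 2.145/0.866) = 0.007 |
| 0.7 | 0.18 SD | P(Z > 0.945/0.714) = 0.093 | P(Z > 2.345/0.714) = 0.0005 |

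Taken over all possible imbalances, the error rate is the nominal 5%.

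**The case against.** The strongest reply is that the stated analysis is valid. In a randomised trial an unadjusted comparison is unbiased over repeated randomisations and keeps its nominal error rate. That stands. A reader might infer that omitting baseline biases the treatment effect or invalidates the test, and the documents do not support this. The shift in step 4 is conditional on the imbalance that occurred, and it can go either way.

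A reader might also quote a much larger error rate. A baseline difference of 0.5 SD favouring the experimental arm would give P(Z > (1.645 − 1)/0.866) = 0.23 at r = 0.5. But a difference of at least that size in that direction has probability P(Z > 2) = 0.023, about 1 trial in 44, and it lies at the point where the baseline t-test would just flag it. It is not a fair picture of the typical case.

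Three further limits stand:

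- Section 14.4 does not say outright that raw follow-up scores were compared. That is the natural reading, not an explicit statement, but step 3 shows that the point survives the change-score reading.
- The size of the gain depends on a correlation that the documents do not give; at r = 0.3 it is modest.
- The chance that some baseline test comes out significant cannot be quantified, because the number of tests is not stated and the outcomes are unlikely to be independent.

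Finally, the trial is complete and its analyses are described in the past tense. Replacing the stated tests would substitute a model chosen after the data were available. That objection governs the form of the fix and leaves the point itself in place.

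**Conclusion.** The point holds as a loss of precision and a conditional shift. The plan collects a baseline value for every outcome and, as written, does not use it in the treatment comparison. The gain forgone ranges from small (9% of residual variance at r = 0.3) to large (49% at r = 0.7), or about 2 to 9 percentage points of power for a single outcome at the back-solved d of 0.74. An unremarkable baseline difference of one standard error moves the unadjusted effect by 0.08 to 0.18 SD. If it favours the experimental arm, the conditional one-tailed error is about 8 to 9%; if it favours the comparator, the error is below 5%. These figures rest on the assumed correlations, on the back-solved effect size for power, and on complete data. They do not show that the sample size of 64 is wrong or that the stated test is invalid.

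**What to change.** For headache pain intensity and each secondary outcome, report an ANCOVA, or a linear mixed model over the two follow-up times, with arm as the effect and the baseline value of the same outcome as covariate. Give the adjusted mean difference with its 95% confidence interval.

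Keep the MANOVA and t-tests visible as the stated analysis, and label the adjusted analysis as added after trial completion. State in Section 14.4 whether the stated tests used follow-up scores or change scores. If the two analyses agree, the result is firmer; if they differ, readers need to know that the conclusion depends on the baseline difference.

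Present baseline data descriptively, and do not offer the p-values from Section 14.3 as evidence of comparability.

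The data were scheduled for collection under Section 10 and the software named in Section 14.4 can fit these models. The cost is one degree of freedom per model and the lower standing of a result labelled post hoc.

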Secondary objectives were to evaluate between-group differences in headache frequency, neck pain intensity, neck-related disability, depression, anxiety, stress, and health-related quality of life at the post-intervention and follow-up assessments.

4. Study Design and Setting

This was a randomized clinical trial with two parallel groups. Participants were assigned to either Passive Physiological Intervertebral Movements plus therapeutic exercise or therapeutic exercise alone. The study was conducted in outpatient physiotherapy settings at Jordan University of Science and Technology and King Abdullah University Hospital. Outcome assessments were collected at baseline, four weeks, and three months.

5. Participant Identification and Eligibility Overview

Participants were screened using a standardized diagnostic process for cervicogenic headache based on clinical history and physical examination. Diagnostic confirmation included assessment of upper cervical dysfunction and symptom behavior consistent with cervicogenic headache. Individuals with contraindications to cervical mobilization or conditions that could confound assessment or treatment were excluded. Full eligibility criteria are entered separately in the ClinicalTrials.gov record.

6. Recruitment

Participants were recruited from physical therapy and rehabilitation services at King Abdullah University Hospital, university students, Ministry of Health hospitals, private physiotherapy centers, and the community. Recruitment approaches included social media advertisements, word of mouth, posters at Jordan University of Science and Technology, and private sector flyers.

7. Randomization and Allocation Concealment

After eligibility confirmation and baseline assessment, participants were randomly assigned to study groups using a random number generator. The randomization process was overseen by an independent researcher who was not involved in diagnosis, treatment, or outcome assessment. Sequentially numbered, opaque, sealed envelopes were prepared before recruitment and used to maintain allocation concealment.

8. Blinding

Outcome assessments were conducted by an assessor who was blinded to group allocation and was not involved in treatment delivery. Due to the nature of the manual therapy intervention, treatment providers were not blinded.

9. Interventions

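### Section 14.4 sets a 5% one-tailed criterion with no justification or stated direction: each t-test is more lenient than a two-sided 5% test, and the MANOVA gate level is left unclear

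*Combined protocol and SAP*

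**What the plan says.** Section 14.4 describes a two-step analysis. First, "Multivariate analysis of variance was used to examine between-group differences in outcome measures at the assessment points". Then, "When multivariate tests were statistically significant, independent-samples t-tests were conducted for individual outcome variables". The next sentence gives the only criterion: "The significance level was set at $p < 0.05$, one-tailed". It exempts no test, gives no reason for one tail, and does not say which tail applies to which outcome.

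Four other places bear on this:

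- **Section 3, objectives.** The primary objective is to determine an effect on headache pain intensity. The secondary ones are also neutral: "Secondary objectives were to evaluate between-group differences in headache frequency, neck pain intensity, neck-related disability", and so on. The only directional wording is in the Section 2 rationale, which asks whether the added movements bring extra benefit over exercise alone.
- **Section 10, outcomes.** There is one primary outcome and eight secondary ones. Lower is better on seven of the nine; higher is better on the two SF-12 component scores.
- **Section 11, sample size.** "Using an effect size derived from a similar study", and "with power of 0.90 and alpha of 0.05, the required sample size was 64 participants, with 32 participants per group". Neither the effect size nor the sidedness of alpha is given.
- **Title block.** Version 1.0 is dated 20 May 2026, the study period ended in August 2025, and the status is "Completed; retrospective ClinicalTrials.gov registration preparation".

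**The concern.** A one-sided test is not wrong in principle. It needs a stated direction, a reason why the other direction is of no interest, and usually a level that does not relax the evidence required for benefit. Section 14.4 supplies none of these.

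Three things are at stake. Results with a one-tailed p between 0.025 and 0.05 count as significant here but would not in a two-sided 5% analysis. If the tail is benefit, the trial cannot declare that adding manual therapy did worse than exercise alone, although neutrally worded objectives leave that possibility open. And the criterion is attached to a passage whose first test, the MANOVA, has no direction. That test decides whether any individual outcome is examined, so a reader needs to know its level.

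**Working it through.** **Inputs.** 32 per arm (Sections 1 and 11); alpha 0.05 one-tailed (14.4); alpha 0.05 with sides not stated, and power 0.90 (11); nine outcomes (10). Assumed, because the documents do not say: the tested tail is benefit, all 64 participants are analysed, and all nine outcomes enter one MANOVA at a time point.

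**1. The plan's own figure.** N = 64 cannot be reproduced without an effect size. It can be solved backwards, d = (z for alpha + z for power) × √(2/32), where √(2/32) = 0.25:

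- One-sided 0.05: (1.645 + 1.282) × 0.25 = 0.73; exact t-test calculation 0.740.
- Two-sided 0.05: (1.960 + 1.282) × 0.25 = 0.81; exact 0.823.

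Both give 32 per arm, so N does not reveal which was used. At d = 0.740, two-sided power with 32 per arm is 0.830 (0.841 by normal approximation), and 0.90 would need 40 per arm. At d = 0.823, two-sided power is 0.90 and one-tailed power is 0.946.

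**2. One t-test alone.** The standard error of a mean difference is SD × √(2/32) = 0.25 SD, on 62 degrees of freedom.

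| Test | Critical t | Smallest significant difference | False claim of benefit |
|---|---|---|---|
| One-tailed 0.05 | 1.670 | 1.670 × 0.25 = 0.42 SD | 5.0% |
| Two-sided 0.05 | 1.999 | 1.999 × 0.25 = 0.50 SD | 2.5% |

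The ratio is 5.0 / 2.5 = 2.

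**3. The MANOVA.** With two groups it is Hotelling's test: T² = (32/2) × D′S⁻¹D, where D is the vector of mean differences and S the pooled covariance matrix. Here F = T² × 54 / (9 × 62) on 9 and 54 degrees of freedom. Replacing D by −D leaves T² unchanged, so the test cannot favour a direction. Compared with 0.05 in the usual way it is a 5% gate; it becomes a 10% gate only if someone halves its p-value.

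**4. The t-test behind the gate.** The sequence was simulated with no true effect on any outcome, nine normal outcomes, 32 per arm, an assumed common correlation of 0, 0.3, 0.5 or 0.7, and 60,000 runs each. Rates are for a false claim of benefit on the primary outcome:

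| Gate and t-test | Range over correlations |
|---|---|
| MANOVA at 5%, t-test one-tailed | 0.65% to 0.71% |
| MANOVA at 5%, t-test two-sided | 0.45% to 0.49% |
| Ratio of these two | 1.40 to 1.51 |
| MANOVA p halved, t-test one-tailed | 1.20% to 1.27% |
| Ratio of the halved case to the two-sided plan | 2.44 to 2.74 |

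If true effects on other outcomes make the MANOVA almost always significant, the gate no longer filters. A primary outcome with no true effect is then tested at 5.0% against 2.5%, and the ratio is 2 again.

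**The case against.** The strongest reply is that the plan never runs a t-test on its own. Behind a 5% MANOVA gate with no true effects, a false primary claim occurs in about 0.7% of trials, well under 2.5%, and the one-tailed choice raises it by less than half again. That stands, and it rules out saying that the plan as a whole doubles the false-positive rate. It does not remove the point: the protection disappears when some of the nine outcomes respond and the gate opens.

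Other stronger readings that a reader might infer also fail:

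- *That the MANOVA gate ran at 10%.* The criterion directly follows the t-test sentence and may have been meant for those tests only. An F test rejects in its upper tail, so an ordinary MANOVA p-value against 0.05 is a plain 5% test. Nothing shows that a p-value was halved. What remains is ambiguous wording.
- *That the document gives no hint of direction.* The rationale does speak of added benefit. The fair complaint is that the objectives are neutral and no tail is assigned per outcome.
- *That Section 11 contradicts Section 14.4.* It is silent on sides, and silence is not a conflict.
- *That one tail was chosen after seeing the data.* The document postdates the study period, so it cannot show that the choice came first. It does not show that it came later either.

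**Conclusion.** The concern holds in limited form. The one-tailed criterion is unjustified and lacks a direction per outcome. Per t-test, if the tail is benefit, it allows 5.0% instead of 2.5% for a false claim of benefit, lowers the bar from 0.50 to 0.42 SD, and rules out a finding of harm. For the primary outcome within the planned sequence, the inflation is a factor of about 1.4 to 1.5 when nothing works and the gate is at 5%, and 2 when effects elsewhere open the gate. The gate's level is ambiguous, not shown to be wrong.

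The 0.42 and 0.50 SD figures assume complete data. Section 14.1 analyses participants with available data, so both thresholds would be somewhat larger after dropout. The simulated ratios rest on assumed normality, correlations and MANOVA composition.

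**What to change.** The trial is complete and Section 14 is in the past tense, so the one-tailed sentence should stay as the record of what was done. Deleting it would hide the criterion used. Add to Section 14.4 and to the results:

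1. Disclose that the criterion was one-tailed, and state the tested direction for each outcome.
2. Report every between-group difference with a two-sided p-value judged at 0.05 and a two-sided 95% confidence interval, and base conclusions on these.
3. Flag any result significant only one-tailed.
4. State that the MANOVA F test is non-directional at 0.05 with an unhalved p-value. If a halved one was used, say so and re-report.
5. In Section 11, report the sidedness and effect size actually used for N = 64. If it was sized one-sided (d about 0.74), restate two-sided power as about 0.83. If two-sided (d about 0.82), it stays 0.90.

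The cost is a few sentences and a second pass through existing output; no new data are needed. For effects in the tested direction, two-sided p-values are twice the one-tailed ones, so some results may lose significance, and the stated power may fall. Baseline adjustment should not be offered as making up the difference. Returning from 0.83 to 0.90 needs a baseline–outcome correlation of about 0.44, since 0.740 / √(1 − 0.44²) ≈ 0.82, and the documents give no correlation.
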